9.3 Demographic and Baseline Characteristics

The following summaries will be provided using the ATS and PP Analysis Set.

The Body Mass Index (BMI) will be defined as body weight [kg]/height [m²].

Medical history and concomitant diseases will be coded by the Medical Dictionary for Regulatory Activities (MedDRA). There will be periodic updates of the MedDRA version. The latest licensed version will be used, and version updates will be implemented upon availability.

- Demographic characteristics (age, race, ethnicity, sex, height, body weight and BMI at Baseline). In addition to summarization as a continuous variable, age will also be categorized and summarized by ≤ 17 years, >17 years, and ≤ 65 years, >65 years.
- HAE History: history of laryngeal attack (yes, no), family history of HAE (yes, no), HAE type (C1-INH type 1, C1-INH type 2), prophylactic HAE therapy within 3 months before Screening (yes, no), number of HAE attacks within 3 months before the start of prophylactic therapy, number of HAE attacks within 3 months before Screening, number of HAE within 3 months before screening for subjects without prophylactic therapy or 3 months before start of prophylactic therapy for subjects with prophylactic therapy.
- Medical history by SOC and PT. This includes medical history terms with end date prior to informed consent date.
- Concomitant diseases by SOC and PT, this includes all medical history flagged as ongoing or with end date after date of informed consent or missing end date.

All demographic and baseline characteristics tables will also be provided for the subset of subjects who used AI.

The following listings will be provided for the ATS:

- Demographic characteristics.
- HAE History.
- Medical history and concomitant diseases.
- Reproductive Findings/Assessment at Screening/Day 1 and additional pregnancy testing throughout the study.

Those listings will further contain a PK and PP Analysis Set inclusion flag.

9.4 Prior/Concomitant Medications and Procedures

Prior/concomitant medications will be coded using World Health Organization Drug Global dictionary (WHODrug Global) B3.

The reported medication will be classified as ‘Prior only’, ‘Prior and concomitant’ or ‘Concomitant only’ in relation to the treatment period.

These 3 categories are mutually exclusive:

- ‘Prior only’: if the subject has not taken any IP; or if the medication end date is before treatment start date.
- ‘Concomitant only’: if the medication start date is on or after treatment start date.
- ‘Prior and concomitant’: if the medication start date/ is before treatment start date and the medication end date is on or after treatment start date.

If medication start and/or stop dates are partially or completely missing, medications will be assumed to be ‘Concomitant Only’, unless there is clear evidence (through comparison of partial dates) to suggest that the medication started prior to the date of the first administration of study treatment. If there is clear evidence to suggest that the medication started prior to the date of first administration of study treatment (the available parts of the date are prior to the corresponding parts of the date of first administration of study), the medication will be assumed to be ‘Prior and Concomitant’, unless there is clear evidence to suggest that the medication stopped prior to the date of the first administration of study (the available parts of the medication end date are prior to the corresponding parts of the date of first administration of study treatment). If this is the case, the medication will be considered ‘Prior Only’.

In addition, ‘Prior only’ medications will be flagged if the end date lies within the run-in period.

Concomitant medications (ie, medication classified as ‘Concomitant only’ or ‘Prior and concomitant’) will be summarized showing the number and percentage of subjects taking

concomitant medications by Anatomical Therapeutic Chemical (ATC) classification level 4 and generic name. If the ATC level 4 coding is not available for a generic name, the next available lower level ATC code will be used.

In the summary of prior and concomitant medications, each subject will be counted once within each unique term. For example, if a subject takes Amoxycillin on 2 separate occasions, the subject is counted only once under the corresponding ATC class.

On-demand HAE medication will be summarized as separate block within the summaries of prior and concomitant medication (as a “virtual” ATC class “On-demand HAE Medication”). The on-demand HAE medication will also be reported in their original ATC class.

Technical Note: On-demand HAE medications prior to Run-in Period are collected in the eCRF form ‘Concomitant and Prior Medications’ with Primary Indication as ‘Study Indication Acute HAE Treatment’. On-demand HAE medications on/after start of the Run-in Period are collected in a separate eCRF form ‘On-demand Treatment’. On-demand medication during the treatment period given for pre-procedure prophylaxis instead of an HAE attack is also documented on the CM and Prior Medication form with the indication “Study Indication (Pre-Procedure/Short Term HAE Prophylaxis”.

For rollover subjects, on-demand HAE medications for attacks that occurred during the Run-in Period of the lead-in study will be imported from the final analysis datasets of the respective lead-in study. Study day will be recalculated to be relative to the reference date for CSL312_3002.

Tables and listings will be provided for ATS.

A listing of prior/concomitant medication will be provided, including the flag for prior medication taken during the run-in period. Non-pharmacological procedures will be listed.

10 Efficacy Analyses

10.1 Analysis of Primary Endpoint

The primary objective of the study is to evaluate the long-term safety of SC administration of CSL312 in the prophylactic treatment of subjects with C1-INH HAE and thus the primary endpoint of the study is a safety endpoint and not an efficacy endpoint. Please see [Section 11.3](#) for a detailed description of the primary safety endpoint and its analysis.

10.1.1 Primary Efficacy Analysis

There is no primary efficacy analysis.

10.2 Analysis of Secondary Endpoints

The secondary efficacy endpoints are:

- Time-normalized number of HAE attacks,
- The reduction in the attack rate during the Treatment Period compared to the Run-in Period,
- The time-normalized number of HAE attacks requiring on-demand treatment,
- The time-normalized number of moderate and / or severe HAE attacks,
- SGART.

10.2.1 Secondary Efficacy Analysis

The secondary efficacy endpoints will be analyzed using the ATS Analysis Set. The endpoint “Time-normalized number of HAE attacks” will also be analyzed using the PP Analysis Set. All efficacy analysis will not differentiate between treatment administration with NSD or AI and will be based on the overall Treatment/Efficacy evaluation period.

Subjects will enter HAE symptoms into their eDiary and the start and end date and time, the interference of HAE symptom(s) with daily activities, and location(s) of the HAE symptom(s). Investigator-reported HAE attacks will be based upon review of subject diaries, relevant interval medical history, and physician judgment. The investigator may ask clarifying questions to assist in his / her assessment of whether an HAE attack occurred. If an attack occurred, the investigator will record an attack in the eCRF, the start/end date, the attack location(s), and the severity of the attack based on the most severe symptoms.

For all analyses considering HAE attacks, only the HAE attacks confirmed and reported by the investigator using the eCRF ‘HAE Attacks’ form will be used.

For CSL312-naïve subjects, HAE attacks with a start date on or after the first day of the Run-in Period but prior to the date and time of the first study drug administration will be counted for the Run-in Period. For subjects from CSL312_2001 and CSL312_3001 the number of HAE attacks in the Run-in Period of the previous study will be used. The HAE attacks that occurred during the Run-in Period of the lead-in study will be imported from the final analysis datasets of the respective lead-in study.

HAE attacks with a start date and time after the first study drug administration through the EOT Visit will be counted for the Treatment Period and will be included in the analyses of efficacy.

HAE attacks will be listed, including start date/time, end date/time, time between start of the attack and end of the most recent preceding attack, anatomical locations, severity, most recent actual CSL312 dose (loading dose of 400 mg or the monthly 200 mg dose), injection device (NSD or AI), potential trigger, duration in days, period in which the HAE attack occurred and how many on-demand medications were taken per HAE attack.

The following derived endpoints based on HAE attacks will be presented together in a listing:

- Time-normalized number of HAE attacks (per month and per year),
- Time-normalized number of HAE attacks requiring on-demand treatment (per month and per year),
- Time-normalized number of HAE attacks with moderate or severe severity (per month and per year),
- Duration of the treatment period,
- Total number of HAE attacks,
- Reduction in Attack Rate (Treatment period versus Run-in),
- Time to first attack (in days),
- Maximum Time between attacks.

Subjects excluded from the efficacy analysis will be presented in a listing, including the reason for exclusion.

Possible reasons for exclusion from efficacy analysis include exclusion from the ATS Analysis Set and insufficient time spent in the study which is defined as a Treatment/Efficacy evaluation period duration of less than 30 days.

10.2.1.1 Time-normalized number of HAE attacks

The time-normalized number (per month) of HAE attacks is calculated per subject as:

$$\frac{\text{the number of HAE attacks}}{\text{length of subject treatment in days}} * 30.4375$$

where the length of subject treatment is calculated as the duration of the Treatment/Efficacy evaluation period described in [Section 8.4](#).

To transform the length of subject treatment which is calculated in days in years the number of days is divided by 365.25. Thus, time-normalized number of HAE attacks per year is calculated per subject as:

$$\frac{\text{the number of HAE attacks}}{\text{length of subject treatment in days}} * 365.25$$

The time-normalized number of HAE attacks will also be calculated for the Run-in Period. For non-CSL312-naïve subjects, the Run-in Period of their previous CSL312 study will be used.

The time-normalized number of HAE attacks per month and per year will be summarized descriptively including median (primary measure of interest) and mean (secondary measure of interest) with corresponding 95% CIs. The CIs for the mean will be based on the t-distribution while distribution-free CIs will be used for the median.

Besides the time-normalized number of HAE attacks, the total number of HAE attacks (ie, not time-normalized) will also be summarized.

10.2.1.2 The Reduction in the Attack Rate during the Treatment Period compared to the Run-in Period

The secondary efficacy endpoint of the percentage reduction in the time-normalized number of HAE attacks is calculated within a subject as:

$$100 * \left(1 - \frac{\text{time normalized number of HAE attacks per month during treatment}}{\text{time-normalized number of HAE attacks per month during Run-in}} \right)$$

and will be summarized descriptively. For non-CSL312-naïve subjects, the Run-in Period of their previous CSL312 study will be used.

The number and percentage of responders and non-responders will be presented combined with corresponding 95% CI. A subject is classified as a responder if the percentage reduction in HAE attacks under treatment compared to the Run-in Period is $\geq 50\%$. In addition, the number and percentage of subjects with percentage reductions of $\geq 70\%$ and $\geq 90\%$ will be presented with corresponding 95% CIs.

Furthermore, the number and percentage of subjects with a percentage reduction of 100%, ie, who are attack-free, will be presented and summarized with corresponding 95% CI.

Wilson confidence intervals will be used to calculate the CIs for percentages.

10.2.1.3 The Time-normalized number of HAE Attacks requiring on-demand treatment

An HAE attack requiring on-demand treatment is identified using the HAE Attack page of the eCRF, where whether on-demand treatment was required is a field to be filled out.

The time-normalized number of HAE attacks per month requiring on-demand treatment is calculated as:

$$\frac{\text{number of HAE attacks requiring on demand treatment during treatment period}}{\text{length of subject treatment in days}} \\ * 30.4375$$

and will be summarized descriptively. To report in years, the number of days will be multiplied by 365.25 instead of 30.4375.

This summary table will also include a categorical breakdown of the used on-demand medication by ATC and PT, including number and percentage of subjects who took a specific medication at least once and the total number of times a specific on-demand medication was used across all subjects. For each on-demand medication by ATC and PT, the number of uses of the on-demand medication per HAE attack will be summarized descriptively.

Both the categorical overview and the time-normalized number of HAE attacks will also be provided for moderate/severe HAE attacks.

The time-normalized number of HAE attacks will also be calculated for the Run-in period. For non-naïve subjects, the Run-in period from the previous study will be used.

10.2.1.4 The Time-normalized number of moderate and / or severe HAE attacks

For the analysis of the time-normalized number of moderate and / or severe HAE attacks, an analogue calculation and analyses will be performed as described in [Section 10.2.1.1](#) using all HAE attacks classified as moderate or severe.

10.2.1.5 Subject's Global Assessment of Response to Therapy

SGART is a patient-reported outcome that represents the subject's overall response to treatment (Question: Considering all of the ways HAE affects you, please rate your response to the study medication you were given to prevent HAE attacks during this Treatment Period.) using the following ratings:

- none – worse or no response at all, not acceptable,
- poor – very little response, not acceptable,
- fair – some response, acceptable but could be better,
- good – good response, acceptable,
- excellent – excellent response, as good as can be imagined.

The SGART response will be provided via electronic Clinical Outcome Assessment (eCOA) data. Missing answers will not be imputed and will be shown as missing.

The SGART results will be presented descriptively by study visit. The number and percentage of subjects with each rating will be presented. In addition, cumulative responses “Poor or better”, “Fair or better”, “Good or Excellent” will be given. For the percentage for cumulative responses a two-sided 95% CI will be presented. The Friedman test will be used to compare the percentage of subjects with good or excellent responses between study Visit Month 12 and study visits Visit Month 24 and Month 36, respectively, including subjects with assessments for both visits being compared. The tests will be exploratory with an alpha of 5%.

A shift table for SGART will also be provided showing the shift between study visits. For each post-baseline visit, the summary table will show the number and percentages for the following:

- Shift from specific response at previous visit to response at current visit (for example, a shift from poor to fair),
- Any improvement,
- Any worsening of the reported outcome.

The responses to SGART will be listed.

10.2.2 Supplementary Analyses of Secondary Endpoints

All secondary efficacy endpoints described above except the SGART will also be assessed over time for 3-month (ie, 91 days) time windows, with the first window starting on the

Day 1 Visit. Subjects will be included in a 3-month window, only if the respective window is completely contained within their Treatment/Efficacy evaluation period.

The time-normalized number of HAE attacks and the time-normalized number of HAE attacks requiring on-demand treatment will also be assessed for the first 31 days of the Treatment Period. This summary will be provided by whether subjects received a loading dose or not. The analyses will also be repeated for attacks, that are moderate or severe. The number and percentage of subjects not experiencing any attacks in the first month will also be displayed.

In addition, 6-month windows will also be provided for the time-normalized number of HAE attacks, where each 6-month window consists of 182 days.

Summaries for cumulative 3-month windows for the time-normalized number of HAE attacks will also be provided (ie, Day 1 to 91, Day 1 to 182, ...). As with other analysis windows, the subject will only be considered if the subject's Treatment/Efficacy evaluation period contains the entire window.

Subject profiles will be generated for each subject. The x-axis will show the Run-in Period and the Treatment Period. The different subject IDs will be plotted on the y-axis. For each subject, a horizontal bar will show the duration of his/her study participation; dots at the respective position of the x-axis will symbolize a mild (white dot), moderate (gray dot), and severe (black dot) HAE attack; an arrow above the bar at a certain position of the x-axis will show the time point when the subject took on-demand medication and an asterisk will show the time of CSL312 administration. In addition, the subject's reason for study discontinuation (if applicable) and a subgroup indicator will be given.

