- Subcutaneous administration of CSL312 dose by investigator or delegate (after completion of physical examination and vital signs). For CSL312 naïve subjects, the first dose of CSL312 will be a loading dose consisting of 2 SC injections of 200 mg CSL312 each for a total dose of 400 mg CSL312. Subjects rolling over from Studies CSL312_3001 and CSL312_2001 will not receive a loading dose. Subjects will complete the Medication Dosing Diary on the eDiary after dosing at the site is complete.
- Record concomitant medications and therapies (type, dose, route, date, and time).
- Record AEs.

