4.2 Study Treatments

There will only be a single treatment arm in this study with the study treatment being CSL312.

All subjects who meet the criteria to enter the study will be assigned to 1 dose of CSL312, 200 mg, to be given SC once monthly for a minimum of 12 doses. For CSL312-naïve subjects, a loading dose of 400 mg (two 200 mg doses) will be administered SC on the first month, then 200 mg once per month in subsequent months. Per original protocol, the dose could have been increased in 200 mg increments for safety reasons and the maximum allowed dose for C1-INH subject was 400 mg per month. The maximum allowed dose for nC1-INH subjects was 600 mg per month. Per Amendment 1, no dosing modifications will be permitted.

No dosing modifications occurred prior to Amendment 1.

All subjects will be trained in CSL312 self-administration at Baseline (Day 1 of the Treatment Period). Subjects who participated in Study CSL312_3001 and subjects naïve to CSL312 will also be trained in CSL312 self-administration at the Month 1, 2, and 3 visits. Starting at Month 4, these subjects will self-administer monthly at home. Subjects who participated in Study CSL312_2001 will have the first dose administered at the site and will self-administer CSL312 at home thereafter. Subjects will complete a medication dosing electronic diary (eDiary) for all doses administered, including doses administered at the site.

Per Amendment 1, subjects or caregivers will SC administer CSL312 200 mg autoinjector (AI) instead of CSL312 200 mg needle safety device (NSD). The first administration with CSL312 200 mg AI will be on site, and training will be provided for subjects and caregivers. Additional CSL312 200 mg AI administration training at subsequent scheduled onsite visits may be provided if it is requested. Subsequent administrations with CSL312 200 mg AI will occur at home (either self-administered or with the help of a caregiver).

The dose and dosing regimen will continue to be 200 mg once monthly. Subjects who decline switching to CSL312 200 mg AI and who have participated in the study for at least

12 months will receive 1 more dose of CSL312 200 mg NSD at the time of the scheduled site visit and subsequently proceed with the EOT Visit 1 month later, as well as a Follow-up Visit 2 months after the EOT Visit, as per the original protocol.

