8.3.2 Treatment-naïve and Non-treatment-naïve Subpopulations

The following two subpopulations will be defined:

- Treatment-naïve: Subjects who did not receive CSL312 before the start of this study, including CSL312-naïve subjects and rollover subjects who received only placebo in the CSL312_3001 study. There are no placebo subjects from CSL312_2001, so no subject rolling over from that study will be included in this subpopulation.
- Non-treatment-naïve: Rollover subjects who received CSL312 previously (ie, non-placebo subjects from CSL312_3001 and subjects from CSL312_2001).

In specific tables, the treatment-naïve subjects may be further differentiated into subjects with loading dose (newly enrolled for CSL312_3002) or without loading dose (rollover subjects previously receiving placebo).

The subgroup analyses that will be conducted for those subpopulations are presented in [Table 5](#) (see [Section 17](#)).

The main tables for QoL questionnaires WPAI:GH, TSQM II and AE-QoL will be presented stratified by treatment-naïve and non-treatment-naïve subjects (see [Sections 10.3.2.1](#) and [12](#) for further details). The time-to-event analysis (see [Section 10.3.1](#)) will be performed only for treatment-naïve subjects, with a further break-down of whether they received a loading dose. For these endpoints, this is considered the main analysis, not an additional subgroup analysis.

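### In the first-31-day summary, the no-loading-dose group pools placebo rollovers with subjects already on CSL312, which can mask an early difference by loading dose

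*SAP*

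**What the plan says.** SAP 10.2.2 states that the time-normalized number of attacks, and of attacks needing on-demand treatment, "will also be assessed for the first 31 days of the Treatment Period", and that "This summary will be provided by whether subjects received a loading dose or not". The same paragraph repeats the analysis for moderate or severe attacks and adds the number and percentage of subjects with no attack in the first month. It names no restriction to treatment-naïve subjects.

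The population comes from SAP 10.2.1: "The secondary efficacy endpoints will be analyzed using the ATS Analysis Set". That set includes the rollovers.

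Who is loaded is clear. SAP 4.2: "For CSL312-naïve subjects, a loading dose of 400 mg (two 200 mg doses) will be administered SC on the first month". Protocol 8.6.3.1: "Subjects rolling over from Studies CSL312_3001 and CSL312_2001 will not receive a loading dose". Previous treatment makes no difference to this.

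SAP 8.3.2 draws the relevant distinction. In specific tables, treatment-naïve subjects may be "further differentiated into subjects with loading dose (newly enrolled for CSL312_3002) or without loading dose (rollover subjects previously receiving placebo"). The non-treatment-naïve are "Rollover subjects who received CSL312 previously (ie, non-placebo subjects from CSL312_3001 and subjects from CSL312_2001"). The section requires the treatment-naïve restriction, broken down by loading dose, for the time-to-event analysis; for other tables the breakdown is optional.

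**The concern.** The no-loading-dose group holds two kinds of subject. CSL312_3001 placebo rollovers start CSL312 at 200 mg with no drug on board. The other rollovers come from CSL312 treatment. Protocol 8.6.3.1 and 8.6.4.1 make the last lead-in visit the same day as Day 1 of this study, and Protocol 1.2.3.1 gives a half-life of about 19 days, so these subjects enter with drug still present.

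A reader who sees month-1 attack rates with and without a loading dose will take the table as evidence on loading. The already-treated subjects carry no information on that question, and they lower the rate in the unloaded group if their attack rate is below that of new starters. The same grouping runs through the on-demand, moderate or severe, and attack-free versions.

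**Working it through.** **Plan's own figure.** The documents give no expected result for this summary, so there is nothing to reproduce. What follows is a check of the grouping and an illustration of its effect on group means.

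**Step 1: composition.** Protocol 1.2.3.2 reports 36 completers of CSL312_2001 and 64 subjects randomized in CSL312_3001. These are upper bounds on rollovers: 36 + 64 = 100. SAP 8.3.2 says no CSL312_2001 rollover counts as a placebo subject. The CSL312_3001 allocation is not given, so assume 16 to 32 placebo subjects. With full rollover the placebo share w is 0.16 to 0.32, and 68% to 84% of the group is already treated. If only 60 roll over and 32 of them had placebo, w = 32/60 = 0.53 and 47% is already treated.

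**Step 2: formulas.** Let L be the month-1 rate with loading, NL the rate in placebo rollovers and SS the rate in already-treated rollovers.
- Pooled rate = w × NL + (1 − w) × SS
- Like-for-like difference = NL − L; displayed difference = pooled − L
- If NL > L, the direction reverses only when w < (L − SS)/(NL − SS), which requires SS < L

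**Step 3: illustrative rates from protocol figures.**
- Baseline: the phase 2 means of 0.05 and 0.35 per month with reductions of 98.94% and 91.68% (Protocol 1.2.3.2) imply placebo rates of 0.05/0.0106 = 4.72 and 0.35/0.0832 = 4.21. Allowing for rounding of the means, 4.25 fits both.
- Exposure-response: 50%, 75% and 90% reductions at 1.4, 3.3 and 7.8 µg/mL (Protocol 3.3.2) fit a Hill curve with slope ln 3/ln(3.3/1.4) = 1.28 and ln 9/ln(7.8/1.4) = 1.28.
- The predicted 91% reduction at steady state is read as a single average concentration of 1.4 × (0.91/0.09)^(1/1.28) = 8.53 µg/mL.
- With a 19-day half-life and absorption time ignored, exposure over the first 30 days is 1 − 2^(−30/19) = 0.665 of steady state after 200 mg and 1.331 after 400 mg.

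These give NL = 0.6071, L = 0.2729 and SS = 4.25 × 0.09 = 0.3825 per month. The like-for-like difference is 0.6071 − 0.2729 = 0.3342.

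**Step 4: masking.**

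| w | Pooled rate | Displayed difference | Share retained |
|---|---|---|---|
| 0.16 | 0.4184 | 0.1455 | 44% |
| 0.32 | 0.4544 | 0.1815 | 54% |
| 0.53 | 0.5023 | 0.2294 | 69% |

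With assumed steady-state concentrations of 12 or 16 µg/mL, the retained share for w of 0.16 to 0.32 is 43% to 54%.

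**Step 5: reversal.** In this model SS exceeds L, so reversal is impossible. It appears only if SS is replaced by something lower, keeping NL and L:
- SS = 0.05 (phase 2 mean at 200 mg): pooled rate 0.14 (w = 0.16) to 0.23 (w = 0.32), below L = 0.27. The threshold is (0.2729 − 0.05)/(0.6071 − 0.05) = 0.40.
- SS = 0.20: the threshold is 0.0729/0.4071 = 0.18.
- SS = 0.35: SS is above L, so there is no reversal.

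**The case against.** The summary is supplementary and descriptive. No test, ratio or difference is specified, SAP 10.4 plans no confirmatory test, and no primary or secondary conclusion depends on it. The arithmetic above is for means, whereas SAP 10.2.1.1 makes the median the primary measure. All of this stands, and it limits the weight of the point.

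A like-for-like view is also already planned. SAP 8.3.2 and 10.3.1 analyse time to first attack, and time to first attack after Day 14, in treatment-naïve subjects by loading dose, with Kaplan-Meier curves and life tables. Attack-free status near Day 31 can be read from these. The first-month rates for all attacks, for on-demand treatment and for moderate or severe attacks cannot.

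The authors may have meant the 8.3.2 breakdown, since that is where the SAP defines subjects with and without a loading dose. But 8.3.2 makes it optional outside time-to-event, 10.2.2 does not invoke it, and 10.3.2.1 describes unpooled presentation as an exception to the other analyses. Table 5 does not settle it: the 31-day summary is not listed there, but the table also leaves out analyses done only in a subset.

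A reader might go further and infer that the table will make loading look harmful. The documents do not support that. The reversal case mixes two sources: NL and L come from the exposure-response model, while the 0.05 comes from phase 2 subjects who had an intravenous loading dose. A reader might also infer that the no-loading-dose group is known to be mostly already-treated subjects. That is plausible under full rollover, but the documents give no enrolment by source.

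**Conclusion.** The point holds as a flaw of grouping. On the text as written, the no-loading-dose group combines first-time users with subjects already treated, and this can mask an early difference by loading dose. In the illustration with full rollover, about half of a 0.33 attacks-per-month difference is lost. Reversal is conditional: already-treated subjects would need a clearly lower month-1 rate than loaded subjects, and placebo rollovers would need to be a small enough share of the group.

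The size rests on an assumed placebo allocation, assumed rollover numbers, modelled month-1 rates and equal underlying attack rates across groups. None of these is documented. The finding about the grouping needs none of them. It should be corrected, but it does not threaten the main conclusions of the study.

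**What to change.** Add a sentence to SAP 10.2.2 requiring the 31-day tables in three columns, using the 8.3.2 definitions:
1. treatment-naïve with loading dose;
2. treatment-naïve without loading dose (CSL312_3001 placebo rollovers);
3. previously treated with CSL312.

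Apply this to the total, on-demand, moderate or severe, and attack-free versions. Base any statement about loading on columns 1 and 2 only. Add a footnote that this comparison is small and non-randomized, since it sets newly screened subjects against completers of an earlier trial, and that it supplements the time-to-first-attack analysis.

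The cost is one sentence and one column split. The subgroups are already defined and no new data are needed. The drawback is a small placebo-rollover column with wide intervals. If the database is already locked, the split can be reported in the CSR as a documented departure from the SAP.
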